4.3 Handling of Dropouts or Missing Data

4.3.1 Imputation of Missing and Incomplete Dates/Times

Every effort will be made to collect complete dates for all study assessments. The following date imputation rules will be applied for missing or partial dates:

- If month and year available, set start date to latest of (1st of the month, first dose date), if end date is complete and imputed start date > end date, set imputed start date to end date – 1
- If year available: Set start date to latest of (January 1st, first dose date), if end date is complete and imputed start date > end date, set imputed start date to end date – 1
- If start date is completely missing, set to first dose date, if end date is complete and imputed start date > end date, set imputed start date to end date – 1.

Completely missing time information will be imputed as 00:00. Partially missing time information with missing hour (xx:mm) or minute (hh:mm) part will be imputed as 00:mm or hh:00, respectively. Missing part will be shown as NK in the listings (where NK = Not Known).

If time is not collected and date of assessment is the same as the first dose date, then assessment will be assumed to be collected prior to treatment unless schedule of assessments and protocol indicate planned collection is always after dosing.

Any AEs with incomplete start and end dates/times will be treated as follows:

Adverse events with unknown start and/or end times (but where the date is known) will be imputed with a time of 00:00 h for the tabulations but will be shown as NK: NK in the listings (where NK = Not Known).

Adverse events with completely unknown start dates will be considered as treatment-emergent for the tabulations and will be shown as NK in the listings. Partially complete AE dates will not be imputed in the listings and the available day, month and year components will be used to determine if an adverse event is treatment-emergent taking the first dosing date and end of study date as references.

Imputing partial AE and prior/concomitant medication start dates:

- a) If the year is unknown, the date will not be imputed and will be assigned a missing value.
- b) If the month is unknown, then:
 1. If the year matches the first dose date, then impute to the month and day of the first dose date.
 2. Otherwise, assign 'January'.
- c) If the day is unknown, then:
 1. If the month and year match the first dose date, then impute to the day of the first dose date.
 2. Otherwise, assign '01'.

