Imputing partial AE and prior/concomitant medication stop dates:

- a) If the year is unknown, the date will not be imputed and will be assigned a missing value.
- b) If the month is unknown, then assign 'December'.
- c) If the day is unknown, then impute to the last day of the month.

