4.11.1 Adverse Events

Adverse events (AEs) will be coded using the Medical Dictionary for Regulatory Activities (MedDRA) Version 23.0 and the Common Terminology Criteria for Adverse Events (CTCAE) Version 5.0.

An AE is any untoward medical occurrence in a study patient administered an IMP which does not necessarily have a causal relationship with this treatment. An AE can therefore be any unfavorable and unintended sign (including a clinically significant abnormal laboratory finding), symptom, or

disease temporally associated with the use of an IMP, whether or not considered related to the IMP. Adverse events may include the onset of new illness and the exacerbation of pre-existing conditions.

Other untoward events occurring in the framework of a clinical study will be recorded as AEs, e.g. those occurring during treatment-free periods (including post-treatment Follow-up period), in association with study-related procedures and assessments.

Concomitant illnesses, which existed before entry into the clinical study, will not be considered AEs unless they worsen during the treatment period. Pre-existing conditions will be recorded as part of the patient's medical history.

A treatment-emergent adverse event (TEAE) is defined as an AE that begins or that worsens in severity after at least one dose of the study drug has been administered.

Adverse event leading to study discontinuation is defined as an AE ongoing on the date of study discontinuation. Ongoing is defined as an AE started on or before and ended on or after the date of study discontinuation.

Summaries with number and percentage of patients reporting at least one adverse event and the total number of events will be reported by group and overall. Adverse event summaries will be provided separately for adverse events which occur or worsen from first dosing to Day 28 and adverse events which occur or worsen after Day 28.

- An overview on the number and percentage of patients with:
 - Any AE
 - Any AE of Grade 3 or higher
 - Any TEAE
 - Any TEAE of Grade 3 or higher
 - Any serious AE (SAE)
 - Any serious adverse drug reaction (SARs)
 - Any suspected unexpected serious adverse reaction (SUSARs)
 - Any treatment-emergent SAE
 - AE leading to death
 - TEAE leading to death
 - TEAE leading to treatment withdrawal
 - Any AE leading to study discontinuation

- TEAE leading to study discontinuation

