4.11.2 Deaths, Serious Adverse Events, and Other Significant Adverse Events

Other significant adverse events are those adverse events reported as leading to an intervention e.g. withdrawal from study, discontinuation of study treatment, introduction of concomitant medication, dose reduction. Following the specification provided for adverse AE summaries at section 4.11.1 summaries detailed below will be provided for deaths, SAEs and other significant AEs:

- Number and percentage of patients for each TEAE leading to death, categorized by SOC and PT
- Number and percentage of patients for each treatment-emergent SAE, categorized by SOC and PT
- Number and percentage of patients for each TEAE leading to study discontinuation, categorized by SOC and PT
- Number and percentage of patients for each TEAE leading to treatment withdrawal, categorized by SOC and PT

For deaths, SAEs and other significant AEs the following listings will be provided:

- A by-patient listing of all deaths that occurred during the study
- A by-patient listing of all serious treatment-emergent adverse events
- A by-patient listing of all TEAE leading to treatment withdrawal
- A by-patient listing of all TEAE leading to study discontinuation

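### Latest-date imputation of partial AE stop dates, combined with a date-only definition, labels some events that ended before exit as leading to study discontinuation

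*SAP*

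**What the plan says.** SAP 4.3.1 gives three rules for partial AE and medication stop dates:

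- Year missing: "If the year is unknown, the date will not be imputed and will be assigned a missing value".
- Month missing: "If the month is unknown, then assign 'December".
- Day missing: "If the day is unknown, then impute to the last day of the month".

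No upper limit at death, study exit, last contact or data cut-off appears there or elsewhere in the SAP. The general start-date rules in the same section do carry a bound: "if end date is complete and imputed start date > end date, set imputed start date to end date", less one day. For display, "Partially complete AE dates will not be imputed in the listings".

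SAP 4.11.1 uses AE dates for a classification: "Adverse event leading to study discontinuation is defined as an AE ongoing on the date of study discontinuation". It continues: "Ongoing is defined as an AE started on or before and ended on or after the date of study discontinuation". The revision history shows that this derivation was added in version 5.0, dated 16 June 2021. The flag feeds two rows of the AE overview in 4.11.1. In 4.11.2 it feeds a by-patient listing and this table: "Number and percentage of patients for each TEAE leading to study discontinuation, categorized by SOC and PT".

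**The concern.** Latest-date imputation is usually harmless for an AE stop date, because at most it lengthens a duration. Here the stop date also decides whether an event is reported as having led a patient to leave the study. An event that had already resolved can be moved past the exit date by the imputation rule alone. It is then presented as a reason for leaving, with no clinical record behind that label. Efficacy was removed from the SAP after the futility recommendation, so the safety tabulations are what the report will rest on.

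A second, separate fault is that an uncapped rule can produce impossible stop dates, after the patient's death or after the data were cut.

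**Working it through.** The plan states no figure on this point, so there is nothing to reproduce. The check applies the two rules to calendar dates.

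**Inputs.** Stop-date rules from SAP 4.3.1. Flag from SAP 4.11.1: start ≤ exit and stop ≥ exit. Planned study period of July 2020 to July 2021 from the protocol synopsis. SAP version date of 16 June 2021 from the revision history.

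**Single case.** Exit 20 March 2021, true end 8 March 2021.

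- Recorded as March 2021: imputed to 31 March, and 31 − 20 = 11 days after exit. Flagged.
- Recorded as 2021 only: imputed to 31 December 2021, which is 286 days after exit. Flagged.

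**General argument.** If the day is unknown and the recorded stop month contains the exit date, the imputed stop is the last day of that month, which cannot precede exit. If the month is unknown and the recorded stop year contains the exit date, the imputed stop is 31 December, which cannot precede exit either. In both cases the flag is always set.

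**Enumeration.** Take every exit date from 1 July 2020 to 31 July 2021 (396 days) and every true end 1 to 48 days earlier, dropping ends before 1 July 2020. The 48-day span and equal weight per pair are assumptions.

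- Pairs: 396 × 48 − (48 × 49)/2 = 19,008 − 1,176 = 17,832.
- Day unknown: a month of L days contributes L(L − 1)/2 pairs with end and exit in the same month. Eight months of 31 days, four of 30 and one of 28 give 8 × 465 + 4 × 435 + 378 = 5,838. All 5,838 are flagged, which is 5,838/17,832 = 32.7% of pairs. The imputed stop falls on average 9.5 days after exit (maximum 29).
- Month and day unknown: only pairs that straddle the new year escape, and there are 1,176 of them. Flagged: (17,832 − 1,176)/17,832 = 93.4%, on average 170 days after exit (maximum 363).

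**How many flags are wrong in the exit month.** Assume the true stop day is uniform over a 31-day month and exit is on the 16th. Every such AE is flagged, and 15/31 = 48% of them had already ended.

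**Effect of a cap.** Capping at exit replaces the imputed date with min(imputed, exit). In the example, min(31 March, 20 March) = 20 March, which still satisfies stop ≥ exit. Over the enumeration the shares stay at 32.7% and 93.4%. Requiring stop > exit as well brings them to 0%, but it also removes the flag from capped events that really were continuing at exit.

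**Future dates.** A stop recorded as 2021 only becomes 31 December 2021. That is 14 + 31 + 31 + 30 + 31 + 30 + 31 = 198 days after the SAP version date, and 31 + 30 + 31 + 30 + 31 = 153 days after 31 July 2021, the planned end of the study.

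**The case against.** Latest-date imputation is a common conservative convention, and the affected set is small. The AE must belong to a patient who left the study, have a partial stop date, have truly ended before exit, and have an exit date inside the recorded stop month or year. AEs are collected only to the D48 visit (Protocol 8), stop date is a required item (Protocol 8.6), and automated checks look for missing data (Protocol 11.2). A year-only stop date would be an extreme case. Reasons for withdrawal are tabulated separately (SAP 4.5.1). The flag drives only two of the 13 overview rows and one of the 11 SOC/PT tabulations. All of this stands and limits the importance of the point.

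The date-only definition is also the larger weakness. Even with complete dates, it counts every AE continuing at exit as leading to discontinuation, whatever the cause. That stands too, and it is why the main correction belongs in 4.11.1.

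Two further replies carry less weight. Listings do show partial dates as recorded, but membership of the discontinuation listing depends on the flag. The SAP does not say expressly that the flag uses imputed dates. However, 4.3.1 holds the only rule for partial AE stop dates, and no other method is given for the flag.

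A reader might infer that the missing cap causes the false flags. The calculation shows otherwise: a stop date capped at exit still counts as on or after exit. The missing cap explains only the impossible dates.

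**Conclusion.** The point holds as a narrow defect of the written rules. Where the recorded stop month or year contains the exit date, an AE that ended before exit is always flagged. The cause is latest-date imputation combined with a test that includes the exit date. The conclusion assumes that the flag is derived from the imputed stop date. The absence of an upper limit is a separate fault that allows dates after death, last contact or cut-off. A death reaches this flag only if it is recorded as a study discontinuation.

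The documents do not give the number of partial stop dates. The 32.7% and 93.4% therefore describe how the rule behaves under the stated assumptions and are not expected counts.

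A reader might go further and conclude that the discontinuation table is materially inflated, or biased between arms. Nothing in the documents supports either: no count is available, and the same rule applies to both arms. Nor is the 198-day figure an effect on any planned table, since no table summarises AE end dates or durations. Seriousness, grade and relatedness do not depend on the stop date. Treatment-emergent status rests on onset or worsening after the first dose.

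**What to change.** 1. In SAP 4.11.1, state that an imputed stop date does not by itself make an AE ongoing at discontinuation. For partial stop dates whose month or year contains the exit date, set the flag from the recorded AE outcome together with the recorded reason for study discontinuation. Both are needed, because an outcome of recovered does not show that recovery came before exit. Outcome is collected under Protocol 8.6, and the discontinuation reason is summarised and listed under SAP 4.5.1.
2. In SAP 4.3.1, set the imputed stop date to the earliest of the last day of the month or year, the date of death, the date of last study contact and the database cut-off. This removes impossible dates but does not by itself correct the flag.

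The cost is a sentence or two in each section and a small programming change. No new data are required. The downside is that the flag for these few AEs then relies on the recorded outcome and reason.

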4.4 Software

All report outputs will be produced using SAS® version 9.4 or a later version in a secure and validated environment.

4.5 Study Patients

4.5.1 Disposition of Patients

A clear accounting of the disposition of all patients who enter the study will be provided, from screening to study completion.

Disposition summaries will be provided by treatment and overall. Number and percentage of patients with ICF, randomized and treated with any amount of study drug will be provided by country and overall). Number and percentage of patients who entered, completed and discontinued (with reason for discontinuation) a study period will be provided separately for treatment and follow up period.

Summary will include:

- the number of subjects randomized
- the number and percentage of subjects treated with any amount of study drug
- the number and percentage of subjects entering, withdrawing from study treatment, withdrawing from the study and completing each phase of the study by treatment group and overall. Withdrawals from the study and from study treatment will also be summarized by major reason.

By-patient listings of eligibility and randomization details, visit dates, and withdrawal details (including reason for discontinuation and duration of treatment prior to discontinuation) will also be provided.

4.5.2 Protocol Deviations

Major protocol deviations are defined as those deviations from the protocol likely to have an impact on the perceived primary efficacy and/or safety of study treatments. The impact of major protocol deviations on the efficacy and/or safety results will be investigated by assessing the robustness of the study results and conclusions to the choice of analysis set, both including and excluding data potentially affected by major protocol deviations.

Major protocol deviations and any action to be taken regarding the exclusion of patients or affected data from specific analyses are defined in the project-specific Protocol Deviation Specification.

Patients with less than 5 continuous days of IP treatment will be considered as a Major Protocol Deviation.

A summary of the number and percentage of patients with a major protocol deviation by treatment will be provided for each country and overall.

By-patient listing of major protocol deviations will be provided.

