6.5. Blinding and breaking the study blind

Study drug will be packaged in blinded high-density polyethylene bottles. Bottles will be numbered according to a randomized treatment number list. The content of the labeling is in accordance with the required references listed in the Good Manufacturing Practices.

The investigator, study personnel, and study participants are blinded with respect to treatment (i.e., active ABX464 or placebo). Sponsor or delegate will generate the random code list and the corresponding treatment number list.

Investigators may have access to unblinding only in case of medical emergency. The code breaks will be available 24 hours a day and 7 days a week using an Interactive Web Response System (IWRS).

The IWRS will require an access code/password/PIN and is only available to staff members delegated by the PI and named on the delegation log of each site.

The investigators and delegated members with unblinding responsibilities are responsible for testing their username and password prior to the treatment of patients to ensure unblinding is possible, or for ensuring appropriately trained staff members are available to action code breaks when required for medical emergencies which may be required out of normal working hours.

Details of any emergency unblinding shall be documented fully in the TMF and Investigator/Pharmacy Site File. The sponsor should be notified of the unblinding and be provided with the patient number but NOT the result. The details shall be included in the statistical report.

However, as there is no antidote, it is highly unlikely that knowledge of treatment would affect the clinical management of the patient. In case of unblinding, the patient will be immediately withdrawn from the treatment phase.

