7.2. Patient Premature trial discontinuation

A patient can be withdrawn at any time from the study. Premature trial discontinuation could occur for the following reasons:

- Investigator's decision.
- An Adverse Event or an intercurrent condition that preclude continuation of treatment. Specifically, an elevation $\geq 3.0 \times$ ULN in liver transaminases (AST/SGOT and/or ALT/SGPT) or Alkaline phosphatase or in total bilirubin compared to baseline requires close observation with repeating liver enzymes and serum bilirubin tests every 2 days. Discontinuation of the study treatment should occur if:
 - ALT or AST $> 8 \times$ ULN
 - ALT or AST $> 3 \times$ ULN and total bilirubin $> 2 \times$ ULN or INR > 1.5
 - ALT or AST $> 3 \times$ ULN with appearance of fatigue, nausea, vomiting, right upper quadrant pain or tenderness, fever, rash, and/or eosinophilia ($> 5\%$).
 - Alkaline Phosphatase $\geq 2.0 \times$ ULN
- Serious adverse event with suspected causal relationship to the IMP
- Any relevant toxicity or negative change in the risk/benefit assessment leading to an unacceptable risk for the patient (i.e. occurrence of adverse events which character, severity or frequency is new in comparison to the existing risk profile), or any data deriving from other clinical trials or toxicological studies which negatively influence the risk/benefit assessment.
- Major protocol violation.
- Withdrawal of consent.
- Administrative reasons from Sponsor.

A patient who prematurely exits the study will not be replaced.

All patients, regardless of the completion or premature discontinuation, should come back for an on-site safety follow-up visit 21 days after the last study drug intake, and all examinations must be performed according to the study flow-chart.

The same long-term follow-up will be performed as described in section 7.1 providing the reason for premature discontinuation is not "withdrawal of consent".

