9.1.2. Definition of study analysis sets

The following datasets will be defined and used for the analyses:

- Enrolled Analysis Set: All patients enrolled in the study will comprise of enrolled analysis set. There will be no safety or efficacy analysis performed on this set.
- Safety Analysis Set: The Safety analysis set will include all the patients randomized in the study and who have received at least one dose of study medication. The safety analysis will be based on the actual treatment received.
- The Full Analysis Set: FAS is defined as all the patients randomized in the study. The efficacy analysis will be based on FAS. The treatment groups will be compared basis the randomized treatment rather than the actual treatment.
- The per protocol (PP) Set: The Per Protocol analysis set will consist of all patients in the FAS without any major protocol deviation (see section 9.1.1). The PP Analysis Set will be used for sensitivity efficacy analyses.

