4.6 Analysis Sets

The following analysis sets will be defined and used for the analyses:

- Enrolled Analysis Set: all patients enrolled in the study. There will be no safety or efficacy analysis performed on this set.
- Safety Analysis Set: all patients randomized in the study to whom study medication has been dispensed. The safety analysis will be based on the actual study treatment dispensed.
- The Full Analysis Set (FAS): all patients randomized. Study treatment groups are defined by the randomized study treatment rather than the actual study treatment dispensed.

Upon database release, protocol deviation and analysis set outputs will be produced and will be sent to ABIVAX for review. An analysis set classification meeting will be arranged to discuss the outputs and to decide which patients and/or patient data will be excluded from certain analyses. Decisions made regarding the exclusion of patients and/or patient data from analyses will be made prior to unblinding and will be documented and approved by ABIVAX.

A summary of the number and percentage of patients assigned to analysis sets will be provided by treatment group and overall, for all enrolled patient.

A by-patient listing of analysis population details will be provided. This listing will be presented by treatment group and will include center, patient identifier, inclusion/exclusion flag for each population, and reason for exclusion from each population.

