4.11 Safety Evaluation

All safety summaries and analyses will be based upon the Safety Set as defined in Section [4.6](#).

By-patient listings will include patient identifier, age, gender and race and will be sorted by patient, safety parameter and visit (if applicable).

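### SAP 4.5.2 labels every patient with under 5 continuous days of drug a major protocol deviator, including early deaths and stops the protocol provides for, and leaves open dropping them from a safety robustness check

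*SAP*

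**What the plan says.** SAP 4.5.2 defines a major deviation as a departure from the protocol likely to affect the perceived primary efficacy or the safety of study treatment. It then adds a rule based on exposure: "Patients with less than 5 continuous days of IP treatment will be considered as a Major Protocol Deviation". No reason for short exposure is exempted.

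The same section gives the label three uses:

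- A summary of patients with a major deviation by treatment, for each country and overall, with a by-patient listing.
- A robustness check of efficacy and/or safety results, "both including and excluding data potentially affected by major protocol deviations".
- Exclusions set elsewhere: "any action to be taken regarding the exclusion of patients or affected data from specific analyses are defined in the project-specific Protocol Deviation Specification". SAP 4.6 adds a meeting before unblinding to "decide which patients and/or patient data will be excluded from certain analyses".

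On the safety analysis itself, SAP 4.11 says "All safety summaries and analyses will be based upon the Safety Set as defined in Section" 4.6. That section defines the set as all randomized patients to whom drug was dispensed, with no exposure or deviation criterion.

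The protocol provides for stopping treatment early. Section 7.2 lists, among other reasons, adverse events, liver criteria, sponsor administrative reasons and "Serious adverse event with suspected causal relationship to the IMP". Section 6.5 says "In case of unblinding, the patient will be immediately withdrawn from the treatment phase". Section 8.3.3 withdraws patients who become pregnant. Protocol 9.1.1 defines major deviations by their liability to bias the primary efficacy endpoint and names non-compliance with study treatment, but has no 5-day threshold.

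**The concern.** A patient who dies on Day 3 has had an outcome. A patient whose drug is stopped on Day 3 for a suspected related SAE has been managed as the protocol provides. Neither has departed from the protocol, yet the 5-day rule records both as major deviators. If the drug causes early stops, the deviation table will show more conduct failures in the active arm when what it is really showing is tolerability.

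The second risk lies in the include/exclude check. Selecting on short exposure is selecting on something that happens after randomization and that treatment can influence. A safety comparison that leaves out early stops and early deaths cannot test whether the safety conclusions are robust to early toxicity, because those cases are the ones taken out.

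**Working it through.** The plan gives no figure for short exposure, so there is nothing to reproduce. The check sets the sections side by side and then bounds the size.

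**Step 1: the rule against the SAP's own definition.**

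| Event before 5 continuous days | Where the protocol deals with it | Departure from protocol? | Label under SAP 4.5.2 |
|---|---|---|---|
| Death | Part of the primary endpoint (2.1) | No | Major deviation |
| AE, related SAE or liver criterion | 7.2 | No | Major deviation |
| Stop of ongoing treatment after a related grade 4 reaction | 3.2 | No | Major deviation |
| Unblinding | 6.5 | No | Major deviation |
| Pregnancy | 8.3.3 | No | Major deviation |
| Sponsor administrative reasons | 7.2 | No | Major deviation |
| Unexplained missed dosing | 9.1.1 (non-compliance) | Yes | Major deviation |

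Only the last row fits a definition that begins from a departure from the protocol.

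**Step 2: where the label leads.**

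- Certain: the by-arm deviation summary and the listing. These depend on no other document.
- Possible: the include/exclude check. SAP 4.13 removes the efficacy endpoints, and SAP 2.2 keeps only the D0 to D48 safety evaluation. In version 5.0, safety results are therefore the only outcome results that this check can act on.
- Not affected: the main safety outputs, because the Safety Set has no deviation criterion.

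**Step 3: what exclusion would do, if applied to whole patients.** Permanent AE stops and deaths before 5 days of dosing would number 0 in each arm of the reduced set, whatever the true rates.

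**Step 4: which stops can fall inside the window.** The first scheduled post-baseline visit is D7 ± 2 days, so the earliest is 7 − 2 = D5. Daily dosing from D0 gives 5 doses by then (D0 to D4); dosing from D1, which protocol 7.1 allows for, gives 4 (D1 to D4). A stop prompted by scheduled liver tests would therefore rarely be caught. The protocol-provided cases most likely to be caught are early deaths, early AEs or SAEs, abnormal unscheduled tests and unblinding.

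**Step 5: size.** Let f be the assumed share of patients with fewer than 5 days for any reason, applied to the planned arms of 533 and 267.

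| f (assumed) | ABX464: 533 × f | Placebo: 267 × f |
|---|---|---|
| 1% | 5.3 | 2.7 |
| 3% | 16.0 | 8.0 |
| 5% | 26.7 | 13.4 |

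Termination could add cases. The documents do not say whether ongoing dosing ended then. If it did, and accrual ran evenly at the planned rate, 800 / (10 × 30.4) = 2.63 patients per day. Patients started in the last 4 days would number 4 × 2.63 = 10.5.

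**Step 6: can the rule be applied as written?** SAP 4.9 derives exposure from the dispensing date to the earlier of return and death. A patient who stops on Day 3 but returns the bottle on Day 28 has a derived exposure of 28 − 1 + 1 = 28 days. These dates do not show whether dosing was continuous, so the rule also needs a stated data source.

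**The case against.** The strongest reply is that little follows from the label. A reader might infer that early deaths and safety stops are removed from the safety analysis. The documents do not support that. The exclusion actions sit in a deviation specification that is not among the documents and in a meeting held before unblinding. SAP 4.5.2 speaks of affected data, not necessarily whole patients. SAP 4.11 lists no deviation-excluded safety table, and 4.6 defines no reduced set. Deaths, TEAEs leading to death and TEAEs leading to treatment withdrawal are all reported on the full Safety Set. All of this stands, and it limits the safety point to an exclusion that the text permits and nowhere rules out. Deciding before unblinding guards against selective choices, but it does not remove the bias of an outcome-dependent rule.

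A reader might also infer that early deaths leave the efficacy sensitivity analysis, since the protocol says "The Per Protocol analysis set will consist of all patients in the FAS without any major protocol deviation". That concerns only the protocol's superseded efficacy plan. SAP version 5.0 has no per-protocol set and no efficacy evaluation, and the protocol's own deviation classification was to be made at a blind-review meeting.

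Nor can the short-exposure group be called mainly toxicity and death. No reasons are reported. Consent withdrawal, poor adherence and drug dispensed but never taken fall under the same rule. Scheduled pregnancy tests are at D0 and D48 only, and protocol 6.3.1 seeks continued dosing in hospital, so worsening alone need not end treatment.

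None of this answers the labelling point. The rule has no exception, and its by-arm table is committed to in the text.

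**Conclusion.** The concern holds in limited form. As written, SAP 4.5.2 reports early deaths and protocol-provided stops as major deviations by arm, which contradicts its own definition of a deviation. It also leaves those patients open to exclusion from a foreseen safety robustness check, which 4.6 and 4.11 neither define nor rule out. The main safety analysis is intact.

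The number affected is unknown: actual enrolment at termination and the reasons for short exposure are not in the documents. The range of about 5 to 27 patients on ABX464 and 3 to 13 on placebo rests on an assumed 1% to 5% share, equal in both arms, at the planned size. It counts all short exposure, so the wrongly labelled patients would be some part of it. The documents do not show that there is an imbalance between arms. A SAP correction is worth making because the wording is clearly at fault and the remedy is small.

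**What to change.** 1. In SAP 4.5.2, limit the 5-day rule to short exposure for reasons other than death, an AE or protocol stopping criterion, unblinding, pregnancy or sponsor termination. Name the data source for continuous days.
2. State there, consistent with 4.6 and 4.11, that no patient is excluded from any safety analysis because of short exposure.
3. Show short exposure by reason and arm alongside the disposition tables. SAP 4.5.1 already summarizes treatment withdrawals by major reason and lists treatment duration before discontinuation.
4. Carry the same wording into the Protocol Deviation Specification.

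The cost is a few sentences in the SAP and a matching change to the specification. The discontinuation reasons are already collected. The only downside is a slightly smaller count of deviators.
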